9.6 Trial Training

All investigators will sign the appropriate Eeva trial-related agreements before they are added to the clinical trial.

Training of trial personnel will be documented on the appropriate training record form and maintained with the site and Merck KGaA trial files which are centrally maintained by the CRO **PPD**. Clinical research staff will be supplied with the clinical protocol, instructions for use, case report form instructions, and other supporting materials.

Topics to be covered at the training may include the following, as appropriate.

- Clinical protocol overview and trial timeframes
- Subject screening and eligibility criteria
- Informed consent procedure
- Eeva instructions for use
- Eeva system malfunctions
- Electronic data capture system, eCRF completion instructions and corrections
- Monitoring procedures
- EC policies and procedures
- Regulatory requirements and compliance

Merck KGaA technical personnel and Monitors (**PPD**) may be present during this trial to provide technical support. Also, an investigators' meeting may be considered prior to the start of the trial for the purpose of trial-related training.

9.7 Required Trial Equipment

The Eeva system will have been previously installed on site for clinical use.

9.8 Site Activation and Supply of Trial Materials

Before a patient is enrolled at a trial site, the investigator must have been initiated and be in receipt of written confirmation (email or letter) from Merck KGaA (or designee) that the site can start. In addition, the following documentation must be on file at Merck KGaA:

- EC favorable opinion/approval letter for the clinical protocol and informed consent documentation (including any subject recruitment materials)
- EC membership list or voting list
- Fully executed Clinical Research Agreement
- Executed Non-Disclosure Agreement (or Clinical Research Agreement)
- Curriculum Vitae (investigator, sub-investigators, research coordinator) – current within 2 years, signed and dated
- Current laboratory certifications, if applicable

Merck KGaA will provide the electronic data capture system. Investigators will be provided with the clinical protocol, training, informed consent information and templates, electronic case report form instructions, and other supportive documents required for the trial.

9.9 Changes to the Clinical Trial Protocol

Changes to the clinical trial protocol will be documented in written protocol amendments. Major (substantial, significant) amendments will usually require submission to the Health Authorities and to the relevant IEC/IRB for approval or favorable opinion. In such cases, the amendment will be implemented only after approval or favorable opinion has been obtained.

Minor (non-substantial) protocol amendments, including administrative changes, will be filed by the Sponsor and at the site. They will be submitted to the relevant IEC/IRB or to Health Authorities only where requested by pertinent regulations.

Any amendment that could have an impact on the subject's agreement to participate in the trial requires the subject's informed consent prior to implementation Clinical Trial Report and Publication Policy

9.9.1 Clinical Trial Report

After completion of the trial, a clinical trial report according to ICH Topic E3 will be written by the Sponsor in consultation with Merck KGaA responsible, the Coordinating Investigator and assigned Medical Writer. An initial report will be generated based on the data that is accumulated when 50% of the subjects have completed the trial with implantation results. Additionally, an interim report will be generated based on the accumulated trial data. The data cutoff date for each report will be pre-specified in its SAP.

The completed trial will be summarized in a final report that accurately and completely presents the trial objectives, methods, results, limitations of the trial, and interpretation of the findings.

9.10 Publication

If the institution or investigator prepares any presentation or publication relating to the trial, the institution or investigator will provide Merck KGaA with a draft of the same for Merck KGaA's review and comment, of which comments the institution or investigator will give due consideration. Merck KGaA will return comments to the institution or investigator within thirty (30) days after receipt of the draft from the institution or investigator. In the event that the institution or the investigator and Merck KGaA differ in their opinion or interpretation of data in the publication, the parties will resolve such differences in good faith through appropriate scientific debate. In addition, the institution or investigator will delay any proposed publication/presentation an additional sixty (60) days, in the event Merck KGaA so requests, to enable Merck KGaA to secure patent or other proprietary protection.

The first publication will be a publication of the results of the analysis of the primary endpoint(s) that will include data from all trial sites.

The Investigator will inform the Sponsor in advance about any plans to publish or present data from the trial. Any publications and presentations of the results (abstracts in journals or newspapers, oral presentations, etc.), either in whole or in part, by Investigators or their representatives will require pre-submission review by the Sponsor.

The Sponsor will not suppress or veto publications, but maintains the right to delay publication in order to protect intellectual property rights.

10 Intellectual Property

During the term of this trial and thereafter, Institution, its employees, agents, subcontractors or affiliates will not disclose confidential information (other than to Merck KGaA or Merck KGaA-designated parties) without Merck KGaA's prior written consent. "Confidential information" will include the protocol, eCRFs, and all materials and information concerning Merck KGaA and the trial disclosed to the Institution or Investigator by Merck KGaA or developed as a result of conducting the trial, except any portion thereof which:

- Is known to Institution, its employees, agents, subcontractors or affiliates before receipt thereof under this protocol, as evidenced by its written records;
- Is disclosed to Institution, its employees, agents, subcontractors or affiliates after acceptance of this protocol by a third party who has a right to make such disclosure in a non-confidential manner; or
- Is or becomes part of the public domain through no fault of the Institution, its employees, agents, subcontractors or affiliates.
- Nothing in this trial will be construed to restrict the Institution or Investigator from disclosing confidential information as required by law or court order or other regulatory order or request,

provided in each case the party requested to make such disclosure will timely inform Merck KGaA and use all reasonable efforts to limit the disclosure and maintain the confidentiality of such confidential information to the extent possible. In addition, the disclosing party will permit Merck KGaA to attempt to limit such disclosure by appropriate legal means.

- Further, during the term of this protocol and thereafter, the Institution, its employees, agents, subcontractors or affiliates will not use the confidential information for any purpose other than that indicated in this protocol and the clinical research agreement without Merck KGaA's prior written approval.
- Institution, its employees, agents, subcontractors or affiliates will not disclose to Merck KGaA any information which is confidential or proprietary to a third party unless Institution has first obtained the prior written approval of both such third party and Merck KGaA.

11 Trial or site Discontinuation

The Sponsor may temporarily or permanently discontinue the trial at a single site or at all sites for ethical, compliance or other reasons. If this is necessary, the Sponsor will endeavor to provide advance notification to the site. If the site or trial is suspended or discontinued, the Investigator will be responsible for ensuring prompt notification to the EC/IRB. Where required by local regulations, the Sponsor will be responsible for informing the EC/IRB of trial or site discontinuation.

12 Trial Closure

Upon completion (when all subjects enrolled have completed the 5-8 weeks Ultrasound or Clinical Pregnancy data collection requirements or have previously exited the trial, and the eCRFs and queries have been completed) or termination of the trial, Merck KGaA will notify the sites.

14.4	Secondary variables selection of ITT.....	10
14.5	Secondary variables KID.....	10
14.6	Exploratory Variables.....	11
15	Safety Evaluation.....	12
16	References.....	12
17	Used Variables.....	12
18	Table description: principles of reporting.....	15
18.1	Generalities.....	15
18.1.1	Type of table.....	15
18.1.2	Format.....	15
19	List of Tables of the report.....	15
19.1	Randomization.....	15
19.2	Screening.....	16
19.2.1	Inclusion/exclusion :.....	16
19.2.2	Patient Disposition.....	16
19.2.3	Comparison at baseline.....	16
19.2.4	Treatment.....	16
19.2.5	Oocytes Retrieval.....	16
19.2.6	Transfer.....	16
19.2.7	Additional Optional Ultrasound.....	17
19.2.8	device Incident.....	17
19.2.9	Study Exit.....	17
19.2.10	Dates.....	17
19.2.11	Safety.....	17
20	Table format.....	18

3 List of Abbreviations and Definition of Terms

AE	Adverse Event
BP	Biochemical Pregnancy
CP	Clinical Pregnancy
CPR	Clinical Pregnancy Rate
EC	Eeva Conform
Eeva	Early embryo Viability Assessment
EMG	arm treated Eeva + Morphology grading
ENC	Eeva Non-conform
IR	Implantation Rate
ITT	Intent to Treat
KID	Known Implantation Data
MG	arm Morphology Grading only
MP	Multiple Pregnancy
nET	Number of Transferred Embryos
nFS	Number of Foetal Sacs
OP	On Going Pregnancy
OPR	Ongoing Pregnancy Rate
RR	Risk Ratio
SM	Spontaneous Miscarriage
SMR	Spontaneous Miscarriage Rate
TRT	Treatment Variable
UR	Utilization Rate

4 Purpose of the Statistical Analysis Plan

Eeva is a time lapse monitoring system able to picturing embryos every 5 minutes during embryo culture and embryo development. The standard technique (Morphology Grading MG) is based on multiple observations of embryos under regular light microscopes, known of limited predictive value: In a Trial, from 2 embryos chosen by MS, 39% , 38% and 23% of cycles resulted in none, one and two blastocysts, respectively. The benefits demonstrated during the first investigations of Eeva is a specificity of 85%. (Eeva should detect 85% of transferred failed embryos). The purpose of this plan is the evaluation of the Early Embryo Viability Assessment (Eeva) efficacy in predicting confidence intervals for relative embryo implantation potential over baseline outcomes

5 Summary of Clinical Study Features

5.1 Primary endpoint

The primary objective of the trial is the point and relative interval estimate of the Implantation Rate (IR) performed on day 3 or day 5 (with and without genetic analysis) in the groups Eeva plus MG (EMG) and MG alone (MG)

5.2 Secondary endpoints

- (a) Utilization Rate (UR) (number of transferred and frozen embryos divided by number of normally fertilized oocytes x 100),
- (b) Clinical Pregnancy Rate (CP) (assessed by ultrasonography at weeks 5 to 8),
- (c) Ongoing Pregnancy Rate (OP) (assessed by ultrasonography at weeks 10 to 12),
- (d) Multiple Pregnancy Rate (MP) (assessed by ultrasonography at weeks 5 to 8) and
- (e) Spontaneous Miscarriage (SM).
- (e) Drugs protocol type (GnRH agonist/GnRH antagonist) and gonadotrophin dose for Controlled Ovarian Stimulation in relation with Eeva categories and implantation outcomes.

5.3 Selection of Trial Population and randomization

See protocol section 5.3 and 5.6

5.4 Documented variables

5.4.1 Screening and treatment

Inclusion Criteria, Age, Pregnancy History , Number of attempts , Number of Spontaneous abortions, Number of Live Births , Number of Non-ART cycles, Number of Fresh ART cycles, Number of Frozen ART cycles, Follicle Stimulating Hormone Maximum, Follicle Stimulating Hormone Units, Anti Mullerian Hormone Max, Anti Mullerian Hormone Unit, Estradiol Max, Estradiol Units, Luteinizing Hormone Max, Luteinizing Hormone Units, Antral Follicle Count ,

Male Infertility, Polycystic Ovaries, Reduced Ovarian Reserve, Tubal Factor , Unexplained, Other.

Treatment variables: Protocol of Stimulation, stimulation medication, Time of hCG trigger to oocyte retrieval, Pre-trigger Endometrium (Trt Set).

5.4.2 Oocyte Retrieval

Number of oocytes retrieved; Andrology information; Insemination method; Total number of normally fertilized eggs (2PN); Culture conditions (including gas phase, media, and protein, etc.); Embryo morphological grading may be assessed on Day 2 as per local laboratory standard practice in those subjects randomized to the Morphology group only.

5.4.3 Embryo Day 3

Type of Eeva Petri Dish (number of micro-wells); Eeva micro-well identification; Cell stage and Morphology grading; Eeva results; Fate of each embryo (Transferred, Cryopreserved, Discarded or extended culture to Day 5/6); Eeva Petri Dish and Scope information; Culture conditions.

5.4.4 Embryo Transfer

Date and day of transfer; Luteal phase support; Use of ultrasound; Final number of embryos transferred.

5.4.5 Embryo Day 5-6

Type of Eeva Petri Dish (number of micro-wells); Eeva micro-well identification; Development stage and Morphology grading; Fate of the embryo (Transferred, Cryopreserved, Discarded or extended culture to Day 5/6); Eeva Petri Dish and Scope information; Culture conditions

5.4.6 Dates

All date of each stage are available

5.4.7 Post Oocyte Retrieval or Post Transfer Day 12-18

Pregnancy test results, Quantitative hCG, as applicable. If the result of the pregnancy test is negative, the subject will have completed the trial and be exited at that time.

5.4.8 Gestational Age Week 5-8 (Transfer and Treatment Outcome eCRF)

Result of initial pregnancy ultrasound; Number of intrauterine gestational sacs; Number of fetal heartbeats. If the result of the ultrasound is negative (no fetal heartbeat is detected), the subject stops

5.4.9 Post-Pregnancy follow-up

Pregnancy outcome

5.4.10 Additional Ultrasound > 8 weeks (Optional)

Result of initial pregnancy ultrasound; Number of fetal sacs and number of fetal heartbeats

5.4.11 Assessment of Safety

Safety of Eeva will be evaluated by assessment of device deficiency only. Each individual occurrence will be listed.

6 Sample Size/Randomization

See protocol 5.3

7 Overview of Planned Analyses

7.1 Sequence of Analysis

One sequence

7.2 Interim Analysis

Interim analysis was planned when half of the patients completed the study in the protocol. But based on medical affairs advice it was decided not to conduct the interim analysis.

7.3 Final Analysis

See section 8 below

Changes to the Planned Analyses

No changes

8 Analysis Sets

The following sets of subjects will be considered in the analysis:

8.1 Intention-to-treat (Full Analysis Set)

The intention-to-treat population includes all randomized subjects. Due to the fact that this is an exploratory trial in contrast to usual definitions of ITT ('presented as randomized') subjects will be presented based on the method used (EvMG = Eeva scores plus morphology grading, MG=morphology grading only).

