4.1 Primary

The primary objective of the trial is to compare the rate of implantation for Day 3/5 embryo transfers using Eeva scores plus morphology grading versus Day 3/5 embryo transfers using morphology grading only. Implantation rates are calculated by dividing the number of gestational sacs with fetal heart beat identified by ultrasonography at weeks 5 to 8 by the number of embryos transferred on Days 3 or 5.

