7.5 Analysis Sets

The following sets of subjects will be considered in the analysis:

Intention-to-treat (Full Analysis Set)

The intention-to-treat population includes all randomized subjects. Due to the fact that this is an exploratory trial in contrast to usual definitions of ITT (‘presented as randomized’) subjects will be presented based on the method used (Eeva scores plus morphology grading, morphology grading only).

Subgroups of Eeva scores plus morphology grading group

The EEVA Time Lapse system assists the embryologist in improving embryo assessment accuracy. Whether the embryologist follows the recommendation made by the system is the decision of the embryologist. Therefore two subgroups will be considered:

- Subjects form Eeva scores plus morphology grading group for whom the embryologist has followed the recommendation of the Eeva system. As the principle selection algorithm for the test arm of the study the selection of embryos for transfer is based on the recommendations made by the EEVA system.
- Subjects form Eeva scores plus morphology grading group for whom the embryologist has NOT followed the recommendation of the Eeva system. Every effort at the site will be made to keep this case to a minimum of cases as investigators are encouraged to use their technical expertise and follow the EEVA system recommendations. However, on investigators' discretion and patients' best interests it may be decided to exceptionally disregard the system recommendation when such recommendation contradicts the morphological pre-assessment of the embryos.

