8.2 Subgroups EC and ENC within the Eeva plus morphology grading group

The EEVA Time Lapse system assists the embryologist in improving embryo assessment accuracy. Whether the embryologist follows the recommendation made by the system is the decision of the embryologist. Therefore two subgroups will be considered:

(a) Subjects form Eeva scores plus morphology grading group for whom the embryologist has followed the recommendation of the Eeva system (group noted EC or Eeva conform). As the principle selection algorithm for the test arm of the study the selection of embryos for transfer is based on the recommendations made by the EEVA system.

(b) Subjects form Eeva scores plus morphology grading group for whom the embryologist has NOT followed the recommendation of the Eeva system (group noted ENC or Eeva Not conform). Every effort at the site will be made to keep this case to a minimum of cases as investigators are encouraged to use their technical expertise and follow the EEVA system recommendations. However, on investigators' discretion and patients' best interests it may be decided to exceptionally disregard the system recommendation when such recommendation contradicts the morphological pre-assessment of the embryos.

PPD will share the "Embryo Days 2, 3, 5, 6 Laboratory Data Morphological/EEVA Grading" data with Merck after the database lock.

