14.1 Primary analysis

Implantation rate will be analyzed with two definitions

First definition: The IR (at embryo level) corresponding to a group of patients is calculated as the ratio of the total fetal sacs (nFS) identified by ultrasonography at weeks 5 to 8 divided by the number of embryos transferred (nET), thus $IR = nFS/nET$.

Alternative Definition of Implantation Rate: The previous (and usual) calculation of IR as mentioned in the protocol ($IR = nFS/nET$) has problems, in particular the implanted embryos are not independent. The international definition used by WHO in particular (see for instance <http://www.advancedfertility.com/ivf.htm>) is: The alternative definition IR^* at women level is $IR_w = nFS_w/nET_w$ and $IR^* = (1/n) \cdot \sum_{w=1,n} IR_w$.

Note: The two definitions IR and IR^* coincide in some cases, in particular for elective Single Embryo transfer eSET (where only one embryo is transferred) or when KID sample is used, but in the general case (ITT sample for instance, IR and IR^* will be different).

The point estimate and 95% CI of IR and IR^* will be calculated in both groups EMG and MG for the ITT selection. No inferential comparison will be conducted between these two groups (as this study is purely descriptive).

The following sections are considered as secondary analyses.

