14.6 Exploratory Variables

Multiple Linear regression analysis of IR (based on subject level) as dependent variable and treatment as independent parameter effected by the following confounding factors

Factors	Description
Stimulation protocol	Categorical variable, 3 states: Agonist Luteal phase; Antagonist; and Agonist Mirco-dose Flare and Other
Drugs used	Categorical variable, 3 states: recombinant Gn, urinary Gn, and mix-use of recombinant and urinary Gns
Day of transfer	Categorical variable, 2 states: D3 Vs D5/6
Age of patients	Continuous variable , years
Culture medium	Categorical variable, 5 states: Quinn's Advanced Fertilization, Global Medium, Vitro life G-IVF, Irvine Single Step Medium, and Other

A better estimate of implantation rate will be obtained based on subject level adjusted for confounding factors by a Multiple Linear regression.

Given the exploratory nature of the design, the model will be investigated stepwise and repeated backward. The final model will exclude backward P-values > 0.10.

The Center effect will also to be considered in the model.

The results of regression analysis will be reported with the following items

- Regression Coefficient with 95% CI
- Standard Error
- P-value
- Coefficient of Determination (R^2)

Subgroup analyses

Further subgroup analysis based on selected baseline parameter could be conducted as follows.

- 1) IR of the two treatment groups at each site (descriptive summary statistics with 95% CI,

and RR with 95% CI and P value). The Risk Ratio, 95% CI and P-value will be calculated, provided the number of subjects in a site will be at least 30, otherwise only descriptive statistics will be provided for that particular site.

- 2) IR, CPR, OPR and SMR of the two treatment groups for subgroups of patients with ET on D3 and D5/6 (descriptive summary statistics, RR with 95% CI and P value);
- 3) IR, CPR, OPR and SMR of the two treatment groups for subgroups of patients with age ≤35 and >35(descriptive summary statistics, RR with 95% CI and P value).
- 4) IR of the two treatment groups for subgroups of patients using 5 types of culture media (descriptive summary statistics, RR with 95% CI and P value).
- 5) IR of subgroups of patients using 5 types of culture media (regardless the method of embryo assessment, descriptive summary statistics and 95% CI)

15 Safety Evaluation

In conformity with protocol, device deficiency will be individually listed.

16 References

No reference at this stage

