Psupp	Protein Supplement	C	4	1= None used, 2 = SPS, 3 = HAS, 4 = SSS, 5 = Other
Negg	N of retrieved eggs	I	6.1	
eggGV	Egg type GV	B		
eggMI	Egg type MI	B		
eggMII	Egg type MII	B		
eggOt	Egg type Other	B		
Trf	Was a transfer attempted ?	B		
Nte	N of transferred Embryos	I	4.1	
Usg	Ultra sound guided	B		1=Yes 2=No
Cat1	Catheter Typ Mucous	B		
Cat2	Catheter Typ Blood	B		
Cat3	Catheter Typ retained embryos	B		
Cat4	Catheter Typ N/A	B		
Grading	Procedure Grading	C	4	1= Easy 2= Difficult
Pdg	Embryo assessed by PGD/PGS	C	4	1=Yes 2=No
Euploid	Euploid transferred ?	B	4	
LPS	Luteal Phase support	B		1=Yes 2=No
DelMet	Delivery Method	C		1= Crinone 2=Endometrin 3=Other Vaginal 4=Intramuscular 5=Other
Test1	Post Transfer test 1	B		1= Urine 2=Blood
Test1r	Post Transfer test 1 result	B		1= Positive 2= Negative
Test2	Post Transfer test 2	B		1= Urine 2=Blood
Test2r	Post Transfer test 2 result	B		1= Positive 2= Negative

US1	Ultra Sound result	B		1= Positive 2= Negative
Nsac	N of gestational Sacs	I	4:1	
Nhbt	N of Heartbeats	I	4:1	
Outc	Final outcome further to Ultra Sound	C		1=No pregnancy 2=Biochemical pregnancy 3=Ectopic 4=miscarriage 5= Ongoing
EndPP	Cycle completed on Per Protocol	B		1=yes 2=o
cycleCSt	IF cycle complete : Status	C		1= Ongoing pregnancy 2= Pregnancy came to term 3= Pregnancy lost 4= Failed to conceive 9= therapeutic abortion 10= Other
cycleNst	If cycle non complete : Status	C		0=Normal 1= OHSS risk 2= Embryo transfer cancelled 5= Freeze all 6= Other 7= Imaging discontinued prior to completion 8= Subject requested to be withdrawn 9= Investigator withdrew subject 10= Subject was lost to follow-up 11= Subject was noncompliant

18 Table description: principles of reporting

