18.1 Generalities

Unless otherwise specified, all these tables are two-way table in subdividing the whole sample following treatment group (trt).

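### The set labelled ITT groups women by method used: no as-randomised estimate is planned, and the method used is undefined when Eeva imaging fails or stops

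*SAP*

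**What the plan says.** Protocol 7.5 and SAP 8.1 agree. Both take all randomised women into a set titled intention-to-treat (Full Analysis Set), say that they depart from the usual definition because the trial is exploratory, and group women by what was done. The protocol's words are "subjects will be presented based on the method used (Eeva scores plus morphology grading, morphology grading only"; the SAP's are "subjects will be presented based on the method used (EvMG = Eeva scores plus morphology grading, MG=morphology grading only".

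SAP 14.1 then states that the primary implantation rates, IR and IR*, "will be calculated in both groups EMG and MG for the ITT selection". SAP 14.4 estimates the secondary endpoints on the same set. The KID sample (SAP 8.3, 14.3, 14.5) is a subset of it and inherits the grouping.

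Overridden recommendations are handled separately. SAP 8.2 keeps in the Eeva group the women "for whom the embryologist has NOT followed the recommendation of the Eeva system (group noted ENC or Eeva Not conform". Stopped imaging appears only as a status code in SAP 17, "7= Imaging discontinued prior to completion", with no rule for group membership.

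SAP 18.1 builds tables by "subdividing the whole sample following treatment group (trt". Neither there nor elsewhere is `trt` defined as randomised arm or method used. The only treatment code given is in the randomisation listing (SAP 19.1).

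**The concern.** Protocol 4.1 sets out to "compare the rate of implantation for Day 3/5 embryo transfers using Eeva scores plus morphology grading versus" transfers using morphology alone, and Protocol 5.5 creates those two groups by randomisation. Grouping by method used lets events after randomisation decide which group a woman is counted in. Part of any EMG–MG difference could then reflect who was moved.

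Two things make this worse. The ITT label invites readers, and planners of the later confirmatory trial, to take the rates as randomised estimates. And the rule is incomplete: for failed, stopped or partial imaging, group membership would be settled at analysis time in an unblinded trial (Protocol 7.13).

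The analyses in SAP 14.6 may also be affected. They include a "Multiple Linear regression analysis of IR (based on subject level) as dependent variable and treatment as independent parameter", and subgroup risk ratios with p-values. Whether these use the same grouping is not stated.

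**Working it through.** **Who can change group.** Women whose embryologist overrode Eeva cannot; they remain in EMG as ENC. Two kinds of women can:

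- *Randomised to Eeva, no usable output.* Protocol 3 says a malfunction costs only the automatic recommendation, and Protocol 5.6 gives every woman's embryos morphological assessment. Such a woman can still have a transfer chosen on morphology alone. Read literally, her method used is MG.
- *Control women assessed with Eeva.* The system is already on site for clinical use (Protocol 9.7) and the trial is unblinded. No passage plans this, but none says how it would be classified.

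**Inputs from the documents.** 1000 Eeva and 500 control women, and a 35% implantation rate, the middle row of the precision table (Protocol 7.2).

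**Assumptions, not in the documents.** No true effect; one embryo per woman; 2–10% of one arm moved; moved women implant at 15–55%.

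**The plan's own figures.** The half-width 1.96·√(p(1−p)/n) at p = 0.35 is 4.18 points for n = 500 and 2.96 for n = 1000, matching the stated 4.2 and 3.0. All ten table entries reproduce to one decimal.

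**Eeva women counted as MG.** Move x women with rate p:

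- EMG = (350 − x·p)/(1000 − x)
- MG = (175 + x·p)/(500 + x)
- EMG − MG = (0.35 − p)·k, where k = x·[1/(1000 − x) + 1/(500 + x)]

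Example, 5% moved at 20%: EMG = 340/950 = 35.79%, MG = 185/550 = 33.64%, difference +2.15 points.

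Spurious difference in points, by the moved women's rate:

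| Moved | k | 15% | 20% | 25% | 35% | 45% | 55% |
|---|---|---|---|---|---|---|---|
| 2% (x = 20) | 0.0589 | +1.2 | +0.9 | +0.6 | 0 | −0.6 | −1.2 |
| 5% (x = 50) | 0.1435 | +2.9 | +2.2 | +1.4 | 0 | −1.4 | −2.9 |
| 10% (x = 100) | 0.2778 | +5.6 | +4.2 | +2.8 | 0 | −2.8 | −5.6 |

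**Control women counted as EMG.** Move y women with rate p:

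- EMG = (350 + y·p)/(1000 + y)
- MG = (175 − y·p)/(500 − y)
- EMG − MG = (p − 0.35)·y·[1/(1000 + y) + 1/(500 − y)]

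For y = 10, 25, 50 (2%, 5%, 10%) the multiplier is 0.0303, 0.0770, 0.1587. At p = 25% the difference is −0.3, −0.8, −1.6 points; at 15% it is −0.6, −1.5, −3.2; at 45% and 55% the signs reverse.

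**Scale.** The 95% half-width for the difference at 35% is 1.96·√(0.35 × 0.65 × (1/1000 + 1/500)) = 5.12 points. Only 10% of the Eeva arm moved with a 20-point gap (±5.6) exceeds it.

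**The case against.** The strongest reply is that little hangs on this. SAP 14.1 calls the study purely descriptive and rules out an inferential comparison of the two groups; the primary outputs are two separate rates. Even in the extreme case they move from 35.0 to 37.2 (EMG) and from 35.0 to 31.7 (MG), inside the planned half-widths of 3.0 and 4.2 points. This limits the consequence, and it stands. It does not remove the defect: the protocol's objective is comparative, Protocol 7.6.2 foresees an exploratory model for the difference, and SAP 14.6 reports treatment coefficients and risk ratios with p-values.

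The departure is also open, prespecified and identical in both documents. That makes it an analysis choice with a misleading label, not a contradiction. Being exploratory, however, is no reason to give up randomised comparability.

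The objective is worded by method, so grouping by method could be called faithful to it. But Protocol 5.5 uses those same descriptions to name the randomised groups.

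Pure device failure should be unrelated to prognosis: Protocol 3 says development is unaffected, and Protocol 5.6 keeps culture conditions the same. This points to the zero-bias column and is a fair argument for that route. It does not cover stopping for other reasons or Eeva use in controls.

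The stopped-imaging code sits under incomplete cycles, so some of these women may have no transfer and add nothing to the implantation rate. That also stands; the malfunction route in Protocol 3 remains.

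Finally, the disposition tables (SAP 10.1, 19.2.2), Eeva conformity (19.2.6) and the device-incident listing (19.2.8) would show some of the switching. None crosses randomised arm with method used.

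**Conclusion.** The concern holds. The set called ITT is as-treated, no as-randomised estimate of the primary or secondary endpoints is specified, and method used has no rule for failed or stopped imaging or for Eeva use in controls.

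The size cannot be fixed from the documents, because neither the number of women who would change group nor their prognosis is given. Under the stated assumptions the spurious difference is 0 at equal prognosis, usually below the 5.1-point sampling half-width, and at most 5.6 points in either direction with up to 10% moved. If few women switch, the two groupings nearly coincide, but no planned table would establish that. This should be fixed; it does not invalidate the trial.

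**What to change.** - In Protocol 7.5 and SAP 8.1, define ITT/FAS as all randomised women, analysed in the arm assigned by randomisation. Use it for the EMG/MG primary, secondary, regression and subgroup tables.
- In SAP 18.1, state that `trt` is the randomised arm.
- Keep method used as a sensitivity set labelled as-treated, with a definition covering failed, stopped or partial imaging and control women assessed with Eeva.
- Add a cross-tabulation of randomised arm by method used.

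The cost is wording in two documents, one cross-tabulation and one extra set of tables. The as-randomised tables need no new data, since the treatment code is already in the randomisation listing (SAP 19.1). The group sizes stay at 1000 and 500, so the protocol's precision table applies unchanged.
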